12.7.5.2 Electrocardiogram Results

Based on the safety analysis set, 12-lead ECG parameters (Heart rate (beats/min), PR interval (msec), QRS duration (msec), QT Interval (ms), QTc B Interval (Bazett's formula) (msec), QTcF (Fridericia's formula) Interval (msec) will be summarized by treatment arm. All ECG results will be listed.

ECG results will be summarized for continuous variables and will be presented for the absolute result and change from baseline (Screening) to D21.

The number and percentage of patient with any abnormal QTcF (as detailed in Appendix 6) values or any other clinically significant ECG abnormality (as defined in Appendix 6) at baseline and within each treatment period will be summarized by treatment arm within the Safety Analysis Set.

12.7.5.3 Columbia-Suicide Severity Rating Scale

The Columbia-Suicide Severity Rating Scale is a patient questionnaire that evaluates suicidal ideation and behaviors. In this study, the C-SSRS is assessed at Screening using the "Baseline/Screening Version" and at subsequent timepoints using the "Since Last Visit" version. At the Screening visit, patient eligibility will be assessed with respect to suicidal ideation during the past month and suicidal behavior during the past 5 years.

The C-SSRS questionnaire is planned to be administered by the investigator (or designee) at Screening, Day 1 H0, Day 15 and D21 of each treatment period and at FU.

To analyze these questionnaires, events will be considered associated with:

- Nabiximols, if collected between first and last date of nabiximols intake.
- Placebo, if collected between first and last date of placebo intake.
- Any unscheduled C-SSRS questionnaire taken during the wash-out period will be linked to the actual treatment arm defined during Period 1.

- FU if collected after last IMP intake and only the latest one will be used for summary.

Derived parameters are presented in [Section 10.23](#).

On treatment and by timepoints assessments

The number and percentage of patients who have answer “Yes” to each of the 5 suicidal ideation subtypes and each of the 5 suicidal behavior subtypes along with the number and percentage of patients presenting:

- A suicidal ideation,
- A suicidal behavior,
- A suicidal ideation or behavior,
- A self-injurious behaviour without suicidal intent.

will be summarized at baseline, for each scheduled on-treatment timepoint, for the 51-day safety on-treatment period, for last on-treatment assessment and for the Follow-up assessment by treatment arm. For this summary FU assessments will be linked to the last treatment received.

Shift table from baseline to maximal suicidal ideation score as well as a shift table for change in category (no suicidal ideation or behavior, suicidal ideation [without suicidal behavior], suicidal behavior) will also be summarized by treatment arm for patients having a baseline and at least 1 post baseline on-treatment assessment.

The number and percentage of patients presenting a suicide-related treatment-emergent event defined as:

- A treatment emergent suicidal ideation (without suicidal behavior) compared to recent history,
- A treatment emergent serious suicidal ideation compared to recent history,
- An emergence of serious suicidal ideation compared to recent history,
- An emergence of suicidal behavior compared to all prior history,

will be summarized by treatment arm.

Observed scores and changes from baseline in Suicidal ideation score and in Suicidal intensity rating score will be summarized at baseline and for each scheduled on-treatment timepoint, for the last on-treatment assessment and for the worst on-treatment score and for the follow-up assessment, by treatment arm using n, mean, median, SD, Q1, Q3, min and max.

Cumulative distribution function on change from baseline to last on-treatment value will be plotted by treatment arm. This will be displayed as an increasing CDF.

Withdrawal assessment from last on-treatment visit

The number and percentage of patients presenting:

- An emergence of suicidal ideation without suicidal behavior,
- An emergence of serious suicidal ideation,
- An emergence of suicidal behaviour.

From last on treatment assessment to FU will be summarized by treatment arm according to last treatment received.

Observed at last on-treatment assessment and FU along with change from last on-treatment assessment in Suicidal intensity rating score will be summarized by treatment group using n, mean, median, SD, Q1, Q3, min and max. A shift table of from last on-treatment to FU score will also be displayed.

For patients with any post-baseline suicidal ideation or suicidal behavior, listings will be prepared including all C-SSRS scores for these patients.

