9.2.15.3 Columbia-Suicide Severity Rating Scale

The definitions of behavioral suicidal events used in this scale are based on those used in the Columbia Suicide History Form. Questions are asked on suicidal behavior, suicidal ideation, and intensity of ideation. At Screening (Visit 1), questions will be in relation to lifetime experiences (baseline). Questioning at all subsequent visits will be in relation to the last assessment (since last visit).

The C-SSRS is to be administered by the investigator or his or her qualified designee at Visits 1 through 10 as indicated in the schedule of assessments (see [Appendix 1](#)); “qualified designee” is defined as anyone who has completed the C-SSRS training within the past 2 years or has continually administered C-SSRS assessments throughout the trial since obtaining the training certificate. The survey should be completed by the same assessor, where possible, throughout the trial. Assessments will be conducted only if patients are capable of understanding and answering the questions, in the investigator’s opinion.

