10.0 Conventions and Derivations

10.1 Study Period, Reference Day, Study Day, Analysis Day and Visit Window

10.1.1 Study Periods

For each patient, there will be a screening period, an evaluable period composed of a treatment period 1, a washout period, and a treatment period 2, and a safety follow-up period.

The Screening period starts on the day of the informed consent signature and ends on Day 1 (as defined on in [Section 10.1.2](#)) before 1st IMP intake.

The evaluable period starts on the day of randomization and ends the day of the safety follow-up visit.

- The **51-day efficacy period** which starts on the first day of IMP administration and ends at the end of treatment date.
 - This period will be composed of:
 - The **21-day on-treatment efficacy Period 1** which starts the day of first IMP intake during Period 1 and ends the earliest between end of Period 1 D21 date and permanent end of treatment date;
 - The on-treatment **wash-out period** which begins the day following the end of the 21-day on-treatment efficacy Period 1 and ends the day before the beginning of the 21-day on-treatment efficacy Period 2;
 - The **21-days on-treatment efficacy Period 2** which starts the day of IRT call for Period 2 and ends on the end of treatment date. This period is only defined for patients exposed to IMP during Period 2.
 - It will be used for efficacy analyses using the Full Analysis Set.
- The **51-day safety period** which starts on the first day of IMP administration and ends at the end of treatment date (+ x days).
 - This period will be composed of:
 - The **21 day on-treatment Safety Period 1** which starts the day of first IMP intake during Period 1 and ends the earliest between end of the wash out period date, the day before the date of IRT call for Period 2, the day before Visit 6 date and permanent end of treatment date + x days.
 - The **21 day on-treatment Safety Period 2** which starts the earliest between date of Visit 6, day of IRT on treatment safety period call for Period 2 date, and ends on the end of treatment day date + x days.
 - x will be equal to 14 days for Adverse events, 4 days for C-SSRS and 0 days otherwise.
 - it will be used for safety analyses using the Safety Analysis Set (unless otherwise specified).
- The **Follow-up period** which starts the day following the 51-day on-treatment safety period and ends on the end of study date.

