12.7 Safety Analyses

The safety analyses will be conducted during the 51-day on-treatment safety period (as described in [Section 10.1](#)) by actual treatment arm. As appropriate, the safety analyses will also be conducted during the follow-up period (as described in [Section 10.1](#)) by treatment sequence. All the safety analyses will be conducted using the Safety Analysis Set.

Some analyses of adverse events and laboratory parameters will assess the potential impact of the study drug among the subgroups presented in Table 12.7-1.

Table 12.7-1 Subgroups applied to Safety Analysis

Group Variables	Subgroup	Comments
Sex	Male Female	
Age group	≤ 18 , > 18 and ≤ 45 ≥ 46 to ≤ 65 > 65	According to patient's distribution within age, age group may be differently defined Detailed derivation is given in Section 10.10
Race	White Black or African American Asian American Indian or Alaska Native Native Hawaiian or Other Pacific Islander Other	According to patient's distribution within race some races may be grouped together
Prior cannabis use	Yes No	If it appears that one patient has missing prior cannabis use information, the missing category will be added for AE summary
Number of current antispasticity medication	0 1 2 ≥ 3	

Patient mean number of daily sprays	≤ 6 sprays, > 6 sprays and ≤ 12 sprays, > 12 sprays.	This is referring to “Patient means number of daily spray” taken during the maintenance phase (derivation as described in Section 10.8.2)
-------------------------------------	--	--

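### C-SSRS forms are assigned to treatment by collection date, not recall interval, and under two conflicting windows, so a patient who stops IMP before the Day 15 (or Day 45) form but stays in the trial can have no on-treatment form

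*SAP*

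**What the plan says.** **Recall and schedule.** Protocol 9.2.15.3 takes lifetime experience at Screening and then states: "Questioning at all subsequent visits will be in relation to the last assessment (since last visit". SAP 12.7.5.3 names the same version of the scale and plans it "at Screening, Day 1 H0, Day 15 and D21 of each treatment period and at FU".

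**Assignment in SAP 12.7.5.3.** A form belongs to "Nabiximols, if collected between first and last date of nabiximols intake", and placebo has the same wording. After the last intake the rule is "FU if collected after last IMP intake and only the latest one will be used for summary". Two additions follow: "Any unscheduled C-SSRS questionnaire taken during the wash-out period will be linked to the actual treatment arm defined during Period 1", and, for the counts by timepoint, "For this summary FU assessments will be linked to the last treatment received". The shift tables take only patients with a baseline form and at least one post-baseline on-treatment form.

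**Assignment in SAP 10.1.1.** The on-treatment safety period ends at end of treatment plus x days, where "x will be equal to 14 days for Adverse events, 4 days for C-SSRS and 0 days otherwise". SAP 12.7 says the safety analyses are run in that period, and the C-SSRS counts in 12.7.5.3 include an entry for it.

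**Patients who stop IMP.** Protocol 4.1 encourages them to remain to the end of the period in which they stop. Protocol Section 10 says that those who must cease IMP should remain in the trial.

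**The concern.** A since-last-visit form describes the days before its own date. Assigning it by that date asks what the patient was taking when the form was filled in, not during the time the answers refer to. For a patient who is off IMP by the date of the form, the two differ. Keeping only the latest form after the last intake then sets aside the one form that asked about the dosing days.

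Suicidality is a named risk in this trial. It appears in exclusion criterion 6.2.21, in the list of reasons to cease IMP (Protocol Section 10), among the adverse events of special interest (SAP Appendices 11 and 12) and as a secondary safety endpoint. Events are likely to be few, so one misplaced form could change how a table reads. Because 12.7.5.3 and 10.1.1 give different windows, two programmers could also produce different tables from the same data.

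**Working it through.** The plan gives no figure to reproduce here. The check runs through every possible last-dose day within a period.

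**Inputs.** Form days come from the Protocol schedule of assessments: Days 1 (predose), 15, 21, 31 (predose), 45, 51 and 58. The two windows come from SAP 12.7.5.3 and 10.1.1. Assumptions: visits on nominal days and no unscheduled forms.

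**Step 1: recall intervals.** 15 - 1 = 14 days; 21 - 15 = 6; 31 - 21 = 10; 45 - 31 = 14; 51 - 45 = 6; 58 - 51 = 7. The first form after the start of dosing therefore comes 14 days later in each period.

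**Step 2: rule.** Let d be the period day of the last dose, v the day of the form and e the extension. A post-baseline form is on-treatment if v <= d + e, with e = 0 under 12.7.5.3 and e = 4 under 10.1.1.
- Day 15 form: d >= 15 when e = 0; d >= 11 when e = 4.
- Day 21 form: d >= 21 when e = 0; d >= 17 when e = 4.

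**Step 3: early last-dose days 1 to 20.** A lost day is a dosing day covered only by a form not classed as on-treatment.

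| Last dose (period day) | SAP 12.7.5.3 (e = 0) | SAP 10.1.1 (e = 4) |
|---|---|---|
| 1-10 | no on-treatment form; all 1-10 dosing days lost | same |
| 11-14 | no on-treatment form; all 11-14 dosing days lost | Day 15 form kept; none lost |
| 15 | Day 15 form kept; no whole day lost | same |
| 16 | Day 15 form kept; 1 day lost | same (16 + 4 = 20 < 21) |
| 17-20 | Day 15 form kept; 2-5 days lost | both forms kept; none lost |

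Stop days with some loss: 14 + 5 = 19 of 20 under 12.7.5.3, and 10 + 1 = 11 of 20 under 10.1.1. Stop days with no on-treatment form at all: 14 and 10.

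**Step 4: visit windows.** With Day 15 moved by 1 day and Day 21 by 2 days either way, the range with no on-treatment form runs from Days 1-13 to Days 1-15 under 12.7.5.3, and from Days 1-9 to Days 1-11 under 10.1.1.

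**Step 5: example.** The last dose is on Day 8 of Period 1 and the patient stays to the end of the period. The Day 15 form covers all 8 dosing days. It is follow-up under 12.7.5.3 (8 < 15) and outside the window of 10.1.1 (8 + 4 = 12 < 15). The end-of-treatment form on Day 21 recalls the 6 days after Day 15. The safety follow-up form, due 7 (+3) days later on Days 28-31, recalls the time after Day 21. Only that last form enters the follow-up summary, and it contains no dosing day.

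**Step 6: recall-interval rule.** If a form counts as on-treatment whenever a dosing day falls after the previous form and on or before its own date, stop days 1-15 are caught by the Day 15 form and 16-20 by the Day 21 form. Stop days with loss: 0 of 20.

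**The case against.** **The 4-day window.** SAP 12.7 refers to Section 10.1, so 10.1.1 may be the operative rule, and last doses on Days 11-14 then keep the Day 15 form. Patients stopping after Day 15 keep that form under either rule. This stands and limits the gap. It does not close it for Days 1-10, and the SAP does not say which section governs.

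**Other outputs.** The emergent-event definitions in SAP 10.23 are not expressly limited to on-treatment forms. Suicidal ideation and behavior is an adverse event category of special interest, attributed by onset up to 14 days after the last dose. Full C-SSRS scores are listed for any patient with a post-baseline event. These are real safeguards, each with a limit. The emergent counts depend on programming. The adverse event tables need the event to be reported as an adverse event, and the SAP does not say that C-SSRS answers become adverse events. Listings give no rate by arm. The follow-up summary is by last treatment but uses only the latest form, and the wash-out rule covers only unscheduled forms.

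**Visit windowing.** SAP 10.1.3 prefers on-treatment safety assessments to off-treatment ones without excluding the latter. That helps when there is a choice of forms. Here the form covering the dosing days is itself the off-treatment one, and 12.7.5.3 tabulates on-treatment timepoints.

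**Stronger readings.** A reader might infer that suicidality in all early stoppers vanishes from every table by treatment. The points above show otherwise. A reader might also apply the 10% dropout assumption to 52 patients and conclude that about 5 are affected. That rate is for leaving the trial, whereas this mechanism needs patients who stop IMP and stay. A patient who leaves on Day 8 and attends the safety follow-up visit 7 (+3) days later has a form on Days 15-18 that reaches back to Day 1 and is tabulated by last treatment. The base of 52 is also superseded by the 68 completers recommended in SAP 8.2. Finally, a reader might infer a downward bias for the treatment that causes more stopping. That is conditional on stop days differing by arm, which the documents do not show. The mandatory stop for suicidality is evaluated with the C-SSRS, so a form exists at that point. Postdose PK samples at Visit 4 imply a dose that day, which would normally make a Day 15 form that triggers stopping on-treatment under both sections. The sections differ on that form only if no dose was taken that day.

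**Conclusion.** The point holds within limits. SAP 12.7.5.3 and 10.1.1 conflict on the C-SSRS window, and assignment by collection date does not match the recall of the form. For a patient who stops before the Day 15 (or Day 45) form and stays in the trial, the form covering all dosing days is excluded from the on-treatment counts by arm, drops out of the follow-up summary, and leaves the patient outside the shift tables. This applies to last doses on period Days 1-14 under 12.7.5.3 and Days 1-10 under either section, on nominal visit days and without unscheduled forms. Later stops lose at most the few dosing days after the Day 15 form.

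The number of patients, and the direction and size of any effect on the comparison between arms, cannot be computed because no distribution of stop days is given. The rule should be corrected before unblinding, since it misplaces safety data that the trial already collects. The efficacy analyses are not affected.

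**What to change.** State one C-SSRS rule and use it in both SAP 10.1.1 and 12.7.5.3, replacing the 4-day window and the collection-date rule:

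- A form is on-treatment for an arm if at least one dosing day of that arm falls after the previous C-SSRS form and on or before the form's own date.
- Day 1 of each period counts as after the predose form. A dose on the date of the end-of-period form (Day 21 or Day 51) belongs to that form. This boundary must be written down because Visits 5 and 9 are dosing days. Without it, every completer's Visit 6 predose and Visit 10 forms could become on-treatment; with it, they remain baseline and follow-up.
- A form is follow-up only if its whole recall interval comes after the last dose.
- Summarise the worst follow-up form, not only the latest.

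The cost is SAP wording and a small programming change, with no new data. The downside is that an event after the last dose but within a mixed interval counts as on-treatment. For a safety summary that is the cautious direction, and a table footnote can say so.

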Control Arm	All patients enrolled in the trial will receive both nabiximols and placebo during the 2-way crossover treatment period.

Procedures	
Assessments/procedures at the trial site include the following:
 
• Informed consent, demographics, previous cannabis use, medical history, electronic diary training, and blood THC test (Visit 1)• Eligibility check and urine drug screen (including THC) (Visits 1 and 2 [predose])• Randomization and IMP dosing training (Visit 2 [predose])• Concomitant medications review, AE review, and vital signs measurement (Visits 1, 2, 4, 5, 6, 8, 9, and 10)• Physical examination (including height measurement at Visit 1 only), 12-lead ECG, and clinical laboratory blood sampling (hematology and biochemistry) (Visits 1, 5, and 9)• Examination of oral mucosa (Visits 1, 2 [predose], 4, 5, 6 [predose], 8, 9, and 10)• Body weight measurement (Visits 1, 2 [predose], 6 [predose], and 10)• Dipstick urinalysis and serum pregnancy test (if appropriate) (Visits 1 and 10)• Urine pregnancy test (if appropriate) (Visits 2 and 6 [predose])• PK blood sampling (IMP) at distinct time points (Visits 2, 4, 5, 6, 8, and 9)• MAS assessment (Visits 1, 2 [predose and at 3 hours ± 15 minutes postdose], 5 [3 hours ± 15 minutes after the first spray of the morning dose], 6 [predose and at 3 hours ± 15 minutes postdose], and 9 [3 hours ± 15 minutes after the first spray of the morning dose])• MSSS-88 assessment (Visits 5 and 9)• T25FW test (Visits 2 [predose], 5, 6 [predose], and 9)• C-SSRS assessment (Visits 1, 2 [predose], 4, 5, 6 [predose], 8, 9, and 10)• IMP dosing at the investigational site (Visits 2, 5, 6, and 9)• IMP dispensing (Visits 2, 4, 6, and 8)• IMP collection and compliance review (Visits 4, 5, 8, and 9)
------------	--

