CIOMS	Council for International Organizations of Medical Sciences
COVID-19	Coronavirus disease 2019
CRO	Contract research organization
C-SSRS	Columbia-Suicide Severity Rating Scale
ECG	Electrocardiogram
eCRF	Electronic case report form
EU	European Union
FAS	Full Analysis Set
FDA	Food and Drug Administration
GCP	Good Clinical Practice
GW	GW Pharma Ltd
IB	Investigator Brochure
ICF	Informed consent form
ICH	International Council for Harmonisation
IEC	Independent ethics committee
IMP	Investigational medicinal product
INR	International normalized ratio
IRB	Institutional review board

IRT	Interactive response technology
LLMT-4	Lower Limb Muscle Tone-4
LLMT-6	Lower Limb Muscle Tone-6
MAS	Modified Ashworth Scale
MS	Multiple sclerosis
MSSS-88	Multiple Sclerosis Spasticity Scale
NRS	Numerical Rating Scale
PD	Pharmacodynamics
PI	Principal investigator
PK	Pharmacokinetic
PP	Per Protocol
PRN	As-needed
PT	Preferred term
PVD	Pharmacovigilance department
QoL	Quality of life
R2	Relaxation Index
SAE	Serious adverse event
SAP	Statistical analysis plan
SD	Standard deviation
SOC	System organ class
SUSAR	Suspected unexpected serious adverse reaction
T25FW	Timed 25-Foot Walk
TBL	Total bilirubin
TEAE	Treatment-emergent adverse event
THC	Δ^9 -Tetrahydrocannabinol
ULN	Upper limit of normal
US	United States

Definition of Terms

Term	Definition
Clonus	A clinical manifestation of spasticity described as self-sustained rhythmic involuntary muscular contractions and relaxations in response to a muscle stretch
Completer	A patient who completes both treatment periods
Day 1	The day a patient first receives investigational medicinal product in this trial
End of trial	Last patient last visit or last contact, whichever occurs last
Enrolled patient	Any patient who has provided written informed consent to take part in the trial
International normalized ratio	A calculation made to standardize prothrombin time
Investigational medicinal product	Term used to describe both investigational active product and reference therapy (placebo)
Investigator	Trial principal investigator or a formally delegated trial physician
Lower Limb Muscle Tone-4	A measure of velocity-dependent muscle tone in the lower limbs consisting of the average of the 4 individual MAS transformed scores of knee flexors and knee extensors on both sides of the body

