10.1.3 Target Days and Visit Window

Visit windows are summarized in [Table 10.1-3](#) for efficacy data and urine drug screen collection and, in [Table 10.1-2](#) for all other safety endpoints.

When there are multiple observations within a visit window, the value closest to the target day will be analyzed (as described in [Table 10.1-1](#)).

For safety assessments, on-treatment assessments will be preferred to off-treatment ones.

In case of ties between observations located on different sides of the target, the observation with the earliest date/time will be used. In case of ties between observations located on the same side of the target, (i.e., more than one value for the same day but at different time), the observation with the earliest date/time will be used. However, in case of non-respect of wash-out period, the one done at least 7 days after last Period 1 dosing date will be preferred.

For efficacy, PRO endpoints visit windowing will apply whether patient is on or off treatment.

Table 10.1-1 Longitudinal Assessment – Analysis Day and Target Day

Treatment Period	Visit / Day	Analysis visit	Target Day (defined by period)	Observation used for analysis, if more than one exists
Screening	Visit 1 / Day -28 to -1	Screening	Day -28 to -1	Latest value
Period 1	Visit 2 / Day 1	Day 1	Day 1*	Closest to Target Day But Day 1 H0 should be before 1 st IMP intake and D1H3 should be post IMP intake
	Visit 3 / Day 8	Day 8	Day 8	Closest to Target Day
	Visit 4 / Day 15	Day 15	Day 15	Closest to Target Day
	Visit 5 / D21	D21	D21	Closest to Target Day
Period 2	Visit 6 / Day 31	Day 1	Day 1*	Closest to Target Day But Day 1 H0 should be before 1 st IMP intake and

Treatment Period	Visit / Day	Analysis visit	Target Day (defined by period)	Observation used for analysis, if more than one exists
				D1H3 should be post IMP intake.
	Visit 7 / Day 38	Day 8	Day 8	Closest to Target Day
	Visit 8 / Day 45	Day 15	Day 15	Closest to Target Day
	Visit 9 / Day 51	D21	D21	Closest to Target Day
Follow-up	Visit 10 / Day 58	Day 28	Day 28**	Closest to Target Day

H = Hours; IMP = Investigational medical product.

** Day 1 is based on the date of IRT call within each period*

*** Day 28 relative to the period where IMP is permanently discontinued thus visit is expected between Day 25 and Day 31*

Table 10.1-2 Longitudinal Assessment – Target Day and Visit Window – Part 1

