10.23 Columbia Suicide Severity Rating Scale (C-SSRS)

The C-SSRS scale is composed of 11 items answered Yes or No. Ten of them are ordered in categories as described below to determine the studied endpoints.

5 subtypes of suicidal ideation:

- Category 1 – Wish to be Dead,
- Category 2 – Non-specific Active Suicidal Thoughts,
- Category 3 – Active Suicidal Ideation with Any Methods (Not Plan) without Intent to Act,
- Category 4 – Active Suicidal Ideation with Some Intent to Act, without Specific Plan,
- Category 5 – Active Suicidal Ideation with Specific Plan and Intent.

5 subtypes of suicidal behavior:

- Category 6 – Preparatory Acts or Behavior,
- Category 7 – Aborted Attempt,
- Category 8 – Interrupted Attempt,
- Category 9 – Actual Attempt (non-fatal),
- Category 10 – Completed Suicide.

Last item:

- Self-injurious behavior without suicidal intent.

The C-SSRS also includes a suicidal ideation intensity rating from 1 (least severe) to 5 (most severe).

The following composite endpoints will be assessed based on the categories described above:

- Suicidal ideation (Yes/No): is Yes if one of the categories from 1 to 5 is answered Yes,
- Suicidal behavior (Yes/No): is Yes if one of the categories from 6 to 10 is answered Yes,
- Suicidal ideation or behavior (Yes/ No): is Yes if one of the categories from 1 to 10 is answered Yes,
- Self-injurious behavior without suicidal intent (Yes /No): is Yes if this question is answered Yes.

The following scores will be derived as follows:

- Suicidal ideation score is rating from 1 to 5 the most severe suicidal ideation category answered Yes and is assigned to 0 if categories 1 to 5 are answered No,

- Suicidal ideation intensity rating score (0 to 25) will be defined as the sum of the 5 features described below (ranging from 0 to 5, 0 being the least severe and 5 being the most severe) rated with respect to the most severe type of ideation category,
 - Frequency,
 - Duration,
 - Controllability,
 - Deterrents,
 - Reason for ideation.

Comparative endpoints will also be defined as described below:

Treatment emergent outcomes will include any events that first emerge or worsen, whereas emergent outcomes will refer to outcomes that first emerge.

- Treatment-emergent suicidal ideation compared to recent history (not using C-SSRS taken during screening):
 - Increase from baseline in suicidal ideation score,
 - Increase from last on-treatment visit to follow-up (FU) visit,

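### The C-SSRS withdrawal table covers only the last treatment stopped, so it misses the Period 1 stop of every patient who enters Period 2, although the Visit 6 predose form already covers that interval

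*SAP*

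**What the plan says.** SAP 12.7.5.3, under the withdrawal assessment, counts patients with emergent suicidal ideation, serious ideation or behavior: "From last on treatment assessment to FU will be summarized by treatment arm according to last treatment received". The same section defines the follow-up category: "FU if collected after last IMP intake and only the latest one will be used for summary". The protocol's Definition of Terms includes placebo in IMP, so a completer's last intake is in Period 2. SAP 10.1.3 places the follow-up visit accordingly: "Day 28 relative to the period where IMP is permanently discontinued thus visit is expected between Day 25 and Day 31". There is thus one follow-up per patient.

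The derived endpoints in SAP 10.23 have the same limit. Apart from comparisons with baseline, the ideation definitions use only the interval "Increase from last on-treatment visit to follow-up (FU) visit".

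The protocol schedules the C-SSRS at Visits 1, 2 (predose), 4, 5, 6 (predose), 8, 9 and 10. Under Protocol 9.2.15.3, every form after screening asks about the time since the previous assessment. The Visit 6 predose form therefore covers the washout.

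For forms completed in the washout, SAP 12.7.5.3 has one rule: "Any unscheduled C-SSRS questionnaire taken during the wash-out period will be linked to the actual treatment arm defined during Period 1". It does not mention the scheduled Visit 6 form.

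**The concern.** The SAP includes a specific harm analysis, by arm, of what happens after treatment stops. In a two-period crossover each completer can contribute one nabiximols stop and one placebo stop. As written, each contributes only one. Among completers, nabiximols stops come only from the placebo/nabiximols sequence and placebo stops only from the nabiximols/placebo sequence. Ideation first reported at Visit 6, after stopping nabiximols in Period 1, has no place in the table designed to show it.

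Attribution is also unclear. SAP 12.7.5.3 assigns forms to a treatment by first and last date of intake, and Visit 6 is the first Period 2 dosing date. Under SAP 10.1.1, Safety Period 1 ends no later than the day before Visit 6, and Safety Period 2 can start on the Visit 6 date. Unless the predose form is handled as a period baseline, an event from the washout could be counted under the Period 2 treatment.

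**Working it through.** **1. The plan's own figures.** Protocol 13.1 assumes SD 0.71, difference -0.30, two-sided 5% and 80% power. A paired t calculation gives 46 completers as the smallest number (power 80.07%). With 10% dropout, 46 / 0.90 = 51.1, rounded up to 52, or 26 per sequence. Both figures reproduce. SAP 8.2 later reports a recommendation of 68 completers. The SAP gives no count of stops assessed; the shares below follow from 1:1 allocation.

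**2. Timing of the two post-stop forms.**
- Period 1 stop: the last dose is on the morning of Visit 5 (Day 21 ± 2, so Day 19 to 23). Visit 6 is Day 31 ± 1, so Day 30 to 32. Shortest gap 30 - 23 = 7 days; longest 32 - 19 = 13 days.
- Final stop in completers: Visit 10 is 7 (+3) days after the last dose or Visit 9 (Protocol 9.1.5), so 7 to 10 days.

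**3. Share of nabiximols stops outside the table.** SAP Table 12.5-1 says that Period 2 data are not collected for patients who stop in Period 1. Their last treatment is the Period 1 treatment, so they are assessed at follow-up. Hence:

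share = (nabiximols/placebo patients entering Period 2) / (all nabiximols/placebo patients + placebo/nabiximols patients entering Period 2)

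- No dropout, 26 + 26: 26 / 52 = 50%.
- Three per sequence stop in Period 1 (assumption): 23 / (26 + 23) = 23 / 49 = 46.9%.
- All six dropouts in nabiximols/placebo (extreme assumption): 20 / (26 + 26) = 20 / 52 = 38.5%.
- All six in placebo/nabiximols (extreme assumption): 26 / (26 + 20) = 26 / 46 = 56.5%.
- 68 completers, 34 + 34: 34 / 68 = 50%. If 10% dropout carries over (76 randomized, four per sequence stopping in Period 1): 34 / (38 + 34) = 34 / 72 = 47.2%.

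For placebo the formula is the same with the sequences exchanged. The balanced cases give identical shares and the two extremes swap.

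**4. What this means for precision.** As an illustration (the SAP plans no such interval), take completers only and suppose no event is seen. The one-sided 95% upper bound on the risk is 1 - 0.05^(1/n).

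| Completers | Nabiximols stops in table now | Bound | With both stops | Bound |
|---|---|---|---|---|
| 46 | 23 | 12.2% | 46 | 6.3% |
| 68 | 34 | 8.4% | 68 | 4.3% |

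**The case against.** The strongest reply is that little is hidden. The Visit 6 form is planned as the Day 1 H0 timepoint of Period 2, and SAP 12.7.5.3 lists all C-SSRS scores for any patient with post-baseline ideation or behavior. SAP 12.7.1 links washout adverse events to the Period 1 arm. Suicidal ideation and behavior is an adverse event of special interest (SAP Appendix 11), and Period 1 censoring in SAP 12.7.2.3 runs to the day before Period 2 dosing. That analysis therefore counts the washout as Period 1 risk time, and each completer contributes to both treatments. The withdrawal table itself is descriptive, has no test, and is an SAP addition that the protocol does not require.

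Most of this stands, and it rules out several stronger readings that a reader might infer:
- That suicidality after the Period 1 stop is unassessed or unreported. The forms are collected and listed; the gap is in one table and its matching definitions.
- That exactly half of all nabiximols withdrawals are always missed. Patients who stop in Period 1 and go no further are assessed.
- That the arm comparison is biased. The same rule applies to both treatments.
- That Visit 6 and Visit 10 are interchangeable. Windows of 7 to 13 and 7 to 10 days are only roughly comparable.
- That the 4-day C-SSRS extension in SAP 10.1.1 cuts the washout out of Safety Period 1. That limit runs from permanent end of treatment, which for a patient entering Period 2 falls later.

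The adverse-event route does not fully replace the C-SSRS table. The documents do not say that every positive C-SSRS answer becomes an adverse event, and the Kaplan-Meier plot appears only if more than 5 patients have an event in each arm. Unscheduled washout forms linked to the Period 1 arm do not enter the withdrawal table either, because they precede the last IMP intake.

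**Conclusion.** The point holds as a gap in one planned safety table. For patients who enter Period 2, the stop of the Period 1 treatment is not tabulated: about half of the stops of each treatment, with the range set by how many patients stop in Period 1 and in which sequence. This rests on 1:1 allocation and on reading follow-up as after the final IMP intake, which the SAP wording and the protocol's definition of IMP support. The dropout patterns are assumptions.

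The consequence is a denominator about half of what it could be, and no within-patient contrast, for an outcome where counts may be small. No efficacy result or protocol-specified summary changes. It is worth correcting because the needed data are already collected and the correction is cheap.

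**What to change.** In SAP 10.23 and 12.7.5.3, define the withdrawal assessment per treatment period:
- For patients entering Period 2, compare the last on-treatment Period 1 form with the Visit 6 predose form.
- For the final treatment (including a Period 1 treatment not followed by Period 2), compare the last on-treatment form with follow-up.
- Summarize by the treatment just stopped. Show the two intervals separately as well as pooled, because their windows differ.
- State that events reported on the Visit 6 predose form are not credited to the Period 2 treatment.

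Each completer then contributes one nabiximols and one placebo stop, and the share not covered falls to about zero apart from missing forms. The cost is SAP wording and one derived record per patient, with no new visit, form or patient. The minor downside is pooling slightly different observation windows, which the separate display makes visible.
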